**Inclusion Criteria:**

1. 18-68 years of age
2. SCI >1 year in duration.
3. Level of SCI C4-T2, AIS A & B
4. Gender and age-matched ( $\pm 5$  years) AB controls
5. Euhydration (participants will be instructed to avoid caffeine and alcohol, maintain normal salt and water intake and avoid strenuous exercise for 24 hours prior to study).

**Exclusion Criteria:**

1. known cardiovascular, kidney or untreated thyroid disease;
2. traumatic brain injury (mod-severe)
3. diabetes mellitus;
4. acute illness or infection;
5. broken, inflamed, or otherwise fragile skin;
6. pregnancy;
7. BMI  $>30$  kg/m^2;
8. smoking;

3a. iv) If subjects are patients, will conventional therapy or diagnostic procedures be withheld or modified for the purpose of this study?

No. Conventional therapy or diagnostic procedures will not be withheld or modified for the purpose of this study.

**3b. Multi-Site Studies**

***Not applicable.***

**3c. Possible Risks**

3c. i) List possible hazards to subjects and/or investigative personnel from the procedures, drugs, or isotopes to be employed. What monitoring or other safety precautions will be taken?

**Thermoregulatory Measurement Procedures**

***Skin Temperature Monitoring (Tsk):*** Skin temperature measurement is non-invasive & not associated with risks. However, persons with sensitive skin could find the tape used to secure the thermocouple to be irritating.

***Core Temperature Monitoring (Tcore):*** The Bair HuggerTM Spot OnTM Temperature Monitoring System is non-invasive & not associated with risks. However, persons with sensitive skin could find the thermocouple adhesive to be irritating. Tcore measurement will be performed in subjects with Hi-SCI only (Visits 2 & 3).

***Tympanic temperature:*** is non-invasive and a disposable sleeve is used for each subject. The placement of the ear thermometer may feel uncomfortable.

Sweat rate (SR) is non-invasive & not associated with risks. However, persons with sensitive skin may find the tape used to secure the capsules to the skin to be irritating.

***Thermal Sensation:*** is non-invasive & not associated with any risks.

***Thermal Comfort:*** is non-invasive & not associated with any risks.

**Hemodynamic Measurement Procedures**

***Microvascular Perfusion:*** Microvascular Perfusion (LDF) measurement is a non-invasive measurement and is not associated with risks.

***Brachial Blood Pressure (BP) and Heart Rate (HR):*** Brachial BP and HR measurement is non-invasive & not associated with risks. The subject may feel the pressure of the inflated cuff to be uncomfortable.

**Thermal Challenge**

***Hyperthermia:*** A potential risk to subjects is an increase in Tcore  $\geq 38.0^{\circ}\text{C}$  causing hyperthermia secondary to sitting in a warm thermal chamber at  $35.0^{\circ}\text{C}$  for up to 2 hours. This risk is greater in persons with higher levels of SCI compared to AB controls. The risk of hyperthermia will be minimized in all subjects by

monitoring Tcore continuously throughout the study. Should the subjects' Tcore reach 37.9°C, or if they complete 120 minutes in the warm thermal room, the protocol will be terminated, and subjects will be transferred to a cooler environment (22°C), covered with cool, wet blankets, and given cold liquids. Subjective symptoms of hyperthermia (headache, confusion, dizziness, nausea, feeling faint, etc.) and autonomic dysreflexia (AD) (increased BP, pounding headache, etc.) will also be assessed throughout the procedure, and if subjects are deemed at risk of hypothermia or AD, the protocol will also be terminated. To decrease the risk of AD, participants with SCI will be asked to empty their bladder prior to starting the protocol.

There is a slight risk of heat-induced hypotension. This risk is greater in AB persons because their ability to peripherally vasodilate, in response to heat, remains intact as opposed to their SCI counterparts. This risk will be minimized by monitoring for symptoms of hypotension (systolic blood pressure (SBP) decrease >20 mmHg from baseline levels, dizziness, lightheadedness, etc.) throughout the procedure and if subjects are deemed at risk of hypotension, the protocol will be terminated.

*Cooling Vest:* There is a slight risk of the wet cooling vest irritating the skin. This risk will be minimized by instructing the subject to wear a standard T-shirt between the vest and their bare skin. Another potential risk to subjects is non-freezing cold injury due to wearing the cooling vest for a duration of 2 hours. The risk of non-freezing cold injury is greater in subjects with HI-SCI who have insentient skin. To minimize this risk, all subjects will wear a T-shirt under the vest and safety testing will first be conducted on AB subjects who will be able to determine if the sensation at any time is less (colder) than "cool". If the vest is judged to be "cold" or any area of the vest is "cold", the vest will be promptly removed, and technical adjustments will be made for safety. Only after safety is confirmed in AB subjects, will the vest be used in subjects with HI-SCI. The vest will self-regulate using feedback from multiple sensors to keep any material within its interior surface well above 17°C, which is the threshold necessary to cause a non-freezing cold injury with prolonged exposure. In an abundance of caution, the minimal vest temperature will be limited to  $\geq 20^{\circ}\text{C}$ . The risk of non-freezing cold injury will also be minimized by constant monitoring of skin temperature under the vest by use of skin thermocouples (12 sites in AB, 10 in Hi-SCI). If the temperature under the vest is determined to be  $< 20^{\circ}\text{C}$ , the vest will be promptly removed, and the protocol will be terminated. The risk of non-freezing cold injury to the skin is minimized as the vest will have been fully bench-tested to meet all safety requirements before human subject testing.

*Subject modesty:* Subjects will wear minimal clothing (shorts and T-shirt) during the study to maximize bare skin exposure to the warm temperature. The exposure may exceed the subject's modesty causing potential embarrassment. To minimize this risk, exposure will be limited to the area of the thermal chamber only and to the minimum number of research team members necessary.

Additional unforeseen risks will be minimized by obtaining and reviewing a thorough medical history of prospective participants. Subjects and clinical experts will have the study objectives explained in detail and will be given the opportunity to ask questions about research procedures and the implications of the research. Moreover, study coordinators will be carefully selected that have experience in working with patients with SCI and have formed a good rapport with these individuals. In addition, we have structured the questionnaire to avoid questions about income and service connection, which have raised subject concerns in previous studies (where veterans refused to answer).

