**For AB participants (Visit 1):** Skin thermocouples will be secured at 12 sites on the ventral and dorsal torso (mid-clavicular line from T3 to T10 dermatomes, bilaterally) for collection of skin temperatures (Tsk).

**For participants with Hi-SCI (Visits 2 & 3):** Participants with Hi-SCI will be asked to empty their bladders to minimize risk of AD during the heat stress protocols (*wet vest, no vest*). Skin thermocouples will be secured at 14 sites, 10 skin thermocouples on the ventral and dorsal torso (five on each side) and 4 additional thermocouples on both hands and feet (2 on each side) for distal skin temperatures as an indirect index of sympathetic vasomotor regulation. A disposable forehead skin temperature sensor (Bair Hugger™ Spot On™ Temperature Monitoring System, 3M, Maplewood, Minnesota) will be placed on the orbital bone, above the eyebrow, on whatever side is most comfortable for the participant in order to measure core temperature (Tcore).

**Baseline Collection (BL):** (for all 3 Visits) At the end of the instrumentation period (~30 minutes) at 25°C while seated and wearing only shorts and a standard T-shirt, a baseline (BL) collection of the following parameters will be performed for 15 minutes. Tcore (in persons with Hi-SCI only) and Tsk will be measured continuously. Subjective ratings of thermal sensation, assessed on a 9-point scale (TS) and general thermal comfort on a 6-point scale (TC). HR, BP, blood oxygen saturation, tympanic temperature and 5 minutes of LDF will be measured at 10-minute intervals. BP will be assessed immediately pre and post each LDF interval for calculation of CVC. SR will be measured for 15 minutes continuously.

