**1. Thermal Challenge for Safety and Comfort Study (Phase 1; 1 visit, AB participants only):** AB participants will be fitted with an appropriately sized cooling vest while seated in a wheelchair at the end of BL. Participants will be transferred into a pre-heated (35°C, 35% relative humidity) thermal chamber for 2 hours with the wet cooling vest on full power. Skin temperatures will be continuously measured at multiple sites under the vest. TC and TS will be assessed every 10 minutes. Participants will be queried if they feel any areas of cold-related discomfort or numbness (cold spots), or any other feelings of discomfort from the vest. LDF will be measured as above, but at 20-minute intervals. SR will be measured for 15 minutes every 30 minutes (4 times). HR, BP, blood oxygen saturation and tympanic temperature will be assessed at 10-minute intervals. **Determinants of success for Phase 1:** 1) Skin thermocouple temperatures maintained  $\geq 20$  °C, and 2) subjective ratings of TS not less than “cool” (i.e., not “cold” or “very cold”) on the 9-point TS scale.

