**Table 1: Schedule of Assessments and Procedures**

Measures	Acclimation	BL	Heat
Run Time (min)	30	15	120
Cumulative Time (min)	30	45	165
*Tcore		††	††
Skin Temperatures		††	††
*Sweat Rate		1x	4x
Thermal Sensation	1x	2x	12x
Thermal Comfort	1x	2x	12x
Laser Doppler Flow		2x	6x
Brachial BP, O 2 sat		2x	12x

†† Tcore and skin temperature measurements will be monitored and collected simultaneously throughout the study. \*Tcore and Sweat Rate in persons with Hi-SCI only.

obtained during BL and Thermal Challenge for all visits (**Table 1**). *Tcore*: will be monitored by a disposable forehead skin temperature sensor (Bair Hugger™ Spot On™ Temperature Monitoring System, 3M, Maplewood, Minnesota) in persons with Hi-SCI only. *Skin Temperature (Tsk)*: will be monitored using TX-4 Skin Surface probes and Iso-Thermex Multichannel Thermometer (Columbus Instruments, Columbus, OH). Skin thermocouples will be taped to 12 sites on the anterior and dorsal trunk of the participant. *Microvascular Perfusion (LDF)*: will be measured using laser probes on the skin of both ventral forearms and calves with a Periflux System 5000 Laser Doppler (Perimed, Stockholm, Sweden) for calculation of CVC. *Sweat rate (SR)*: will be measured by the Quantitative Sweat Measurement System (WR Medical Electronics, Stillwater, MN) with capsules secured to 4 sites: left upper arm, left forearm, left mid-thigh, and left midcalf.

**Thermal Sensation (TS) and Thermal Comfort (TC):** TS will be measured by a 9-point thermal sensation scale, while TC will be measured by a 6-point thermal comfort scale (attached). Tympanic temperature will be assessed in all participants using a Braun PRO 6000 infrared ear thermometer (Welch Allyn, Skaneateles Falls, NY).

**Hemodynamic Measurement Procedures:** Brachial BP: BP will be measured at the brachial artery using the Carescape Dinamap V100 Automated BP Monitor (Carescape, Milwaukee, WI). BP will be obtained at 10-minute intervals throughout BL and Thermal Challenge and immediately pre and post LDF measurement for calculation of CVC.

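### The 37.9°C core-temperature heat stop is claimed for all subjects, but core temperature is not measured in the 5 able-bodied Phase 1 participants, who have no temperature-based heat stop

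*Combined protocol and SAP*

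**What the plan says.** All references are to the combined protocol and SAP.

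The Hyperthermia paragraph of Section 3c (Thermal Challenge) claims that "The risk of hyperthermia will be minimized in all subjects" by "monitoring Tcore continuously throughout the study". The trigger for ending the session is "Tcore reach 37.9°C, or if they complete 120 minutes in the warm thermal room". The same paragraph compares the risk in higher-level injury with that in able-bodied controls, so both groups are within its scope.

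Other sections restrict the measurement itself:

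- Section 3c, Core Temperature Monitoring: "Tcore measurement will be performed in subjects with Hi-SCI only (Visits 2 & 3".
- Section 3, Baseline Collection, which covers all three visits: "Tcore (in persons with Hi-SCI only) and Tsk will be measured continuously".
- Table 1, footnote: "Tcore and Sweat Rate in persons with Hi-SCI only".
- The procedure descriptions in Section 3 and in items 3a. i and 3a. ii give the forehead sensor to Hi-SCI participants only.

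For the able-bodied visit, Section 3 (Thermal Challenge for Safety and Comfort Study, Phase 1) provides that "HR, BP, blood oxygen saturation and tympanic temperature will be assessed at 10-minute intervals". It attaches no ear-temperature value to stopping.

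The Phase 2 procedure in Section 3 stops a Hi-SCI session when core temperature rises to 38°C, not 37.9°C.

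**The concern.** The risk section is where ethics reviewers and session staff look for the rule that ends a heat exposure. It offers a numeric, continuously monitored rule for everyone, but the measurement schedule supplies the number for only one of the two groups. The group left out is the one exposed first: Phase 1 is the first human testing of the second prototype, with two hours planned in a 35°C chamber.

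At stake is whether a stated safeguard exists as described, and whether staff have one number to act on. The efficacy comparison is not at stake, because able-bodied participants contribute no core-temperature data to it.

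**Working it through.** The plan gives no figure of its own on this point, so the check sets the relevant sections side by side, with a few counts.

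**1. Does the stop have an input in Phase 1?** The rule needs core temperature. Instrumentation for the able-bodied visit lists torso skin thermocouples, laser Doppler flow, blood pressure and heart rate, sweat rate, pulse oximetry and ear temperature. The forehead sensor appears only in the paragraph for Hi-SCI visits. The rule as written therefore has no data in Phase 1.

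**2. Does anything else supply the stop?**

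- *Ear temperature.* It is read in all participants, and item 3a. ii groups it with the vital signs. No section ties it to termination.
- *Axillary sensors.* Section 4 (Temperature Regulation with Feedback Control) sends an axillary core-temperature signal to the vest's microprocessor. Its thresholds (36.6°C and 35.4°C) switch vest power on and off. The signal is not listed among the able-bodied measurements and is not linked to the 37.9°C rule.
- *Skin temperature.* The 20°C limit protects against cold, not heat.
- *Other stops in Section 3c.* The 120-minute limit, the symptom check and the hypotension stop do not depend on core temperature, so they remain usable.
- *Physician responsibility.* This is set out in general terms under the Phase 2 procedure, with no able-bodied temperature value.

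**3. Size.**

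- Participants without a temperature-based heat stop: 5 of 10 + 5 = 15.
- Ear readings during heat exposure: 120 min / 10 min = 12 per person, and 12 × 5 = 60 in Phase 1, none with a stopping value.
- Prior core-temperature change in able-bodied controls under this type of challenge without a vest (Section 4, Preliminary Studies): −0.1 ± 0.2°C in 19 controls and −0.06 ± 0.2°C in 9 controls. Both means are slightly negative, and Phase 1 adds the wet vest at full power.

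**4. The Hi-SCI threshold.** The difference is 38.0 − 37.9 = 0.1°C, over 10 participants × 2 visits = 20 sessions. Section 3c defines hyperthermia as 38.0°C or above, so 37.9°C stops just before it and 38°C stops at it.

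**The case against.** The strongest reply is that able-bodied participants are not unwatched. Ear temperature, heart rate, blood pressure, oxygen saturation, thermal sensation and thermal comfort are all recorded every 10 minutes, and participants are asked about discomfort. A physician seeing a high ear reading could end the session without a preset number. Earlier controls did not warm on average, and the hazard Phase 1 is built to detect is cold injury, which does have numeric limits. All of this stands, and it is why the point is small.

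The axillary signal also deserves weight. The protocol calls it core temperature, samples it every 5 seconds and gives its offset from rectal temperature as about 1°C. A usable signal may therefore exist for anyone wearing the vest. But no section says staff can read it or that it ends a session. The supportable statement is that no temperature-based heat stop is operational for able-bodied participants as the plan is written, not that none could be devised.

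The Table 1 footnote should not carry the case alone. It also restricts sweat rate to Hi-SCI, whereas the Phase 1 text measures sweat rate in able-bodied participants. The restriction on core temperature is repeated consistently elsewhere, so the conclusion does not depend on the footnote.

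A reader might infer that the symptom stop fails to cover heat, because it is printed as "if subjects are deemed at risk of hypothermia or AD, the protocol will also be terminated". The documents do not support that. The paragraph is about hyperthermia, the sentence lists hyperthermia symptoms, and the Phase 2 procedure pairs autonomic dysreflexia with hyperthermia. It is an evident slip.

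On the two Hi-SCI values, staff who follow both rules will simply stop at the lower one. There is no deadlock, only a threshold that should read the same in both places.

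**Conclusion.** The point holds in a limited form. The risk section credits all subjects with a 37.9°C core-temperature stop that is not operational for the 5 able-bodied participants, and the Hi-SCI stop differs by 0.1°C between two sections. Both are inconsistencies in the current text of a safety rule and are worth correcting before Phase 1.

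The importance is low. A reader might go further and infer that able-bodied participants face a material heat hazard, or that the trial's results are compromised. The documents support neither. The prior control data and the vest's cooling point to very low risk, other stops remain, and no endpoint or analysis uses able-bodied core temperature. No probability of an event is claimed here.

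The conclusion assumes only that the repeated restriction of core temperature to Hi-SCI is intended and that the all-subjects wording in Section 3c is the outlier.

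**What to change.** 1. **One Hi-SCI value.** Use 37.9°C in both Section 3c (Thermal Challenge) and the Phase 2 procedure, since it stops before hyperthermia as Section 3c defines it.

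2. **A rule for able-bodied participants.** Limit the core-temperature claim in Section 3c to Hi-SCI. Then state there and in the Phase 1 procedure that an able-bodied session ends when ear temperature, confirmed by an immediate repeat reading, reaches a stated number. That number should be written into the protocol before Phase 1. The Hi-SCI value should not be carried over without support, because the documents give no ear-to-core offset.

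   *Alternative:* place the same disposable forehead sensor on the able-bodied participants at Visit 1. This makes Section 3c true as written, keeps 37.9°C and avoids the offset question. It costs five sensors and requires amending the statements that restrict the measurement to Hi-SCI.

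3. **Editorial note only.** Change hypothermia to hyperthermia in the symptom-stop sentence.

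With the ear-temperature option, the cost is two sentences and one aligned number, with no new scheduled measurement and only a repeat reading when the value is met. The downside is an occasional false stop. The documents give no error figure for the ear thermometer, so its frequency cannot be estimated from them.

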In 20 persons with Hi-SCI (NLI C4-T4, AIS A-B) who were exposed to the identical warm challenge, we found a greater rise in average  $T_{core}$  than 19 matched AB controls ( $0.6 \pm 0.3^\circ\text{C}$  vs.  $-0.1 \pm 0.2^\circ\text{C}$ ,  $p < 0.001$ , respectively). Thirteen of the 20 (65%) had evidence of greater sympathetic interruption (lower blood pressure and sweat rate than controls) and demonstrated a greater rise in  $T_{core}$  than 7 persons (35%) with Hi-SCI ( $0.8 \pm 0.3^\circ\text{C}$  vs.  $0.3 \pm 0.3^\circ\text{C}$ ;  $p < 0.001$ , respectively) whose blood pressure and sweat rate were not different than controls, despite NLI and AIS grades not being significantly different between the two Hi-SCI groups. The lower blood pressure and decreased sweat rate in 13/20 participants with Hi-SCI signify greater vasomotor disruption, greater sympathetic cholinergic interruption, and the least amount of evaporative heat loss. In support of the significance of these findings in achieving optimal health and QOL, our lab conducted a study assessing subjective comfort during the warmer seasons, which surveyed 100 participants with SCI (50 persons with tetraplegia (C3-C8, AIS A-D), 50 with paraplegia (T1-T12, AIS A-D), and 50 age-matched AB controls (unpublished data). Both tetraplegia and paraplegia groups reported an impaired ability to stay comfortable when compared to the AB group. The negative effect on social activities was greatest in the tetraplegia group. In addition, once feeling overheated, a greater proportion of the participants in the tetraplegic group reported needing significantly more time ( $\geq 20$  minutes) to return to feeling comfortable than those in either the paraplegic or AB groups.

Our “smart” cooling vest is designed to provide a large area of contact with the user with a material that is a good thermal conductor and will be maintained at a uniform temperature  $10-15^\circ\text{C}$  cooler than the user’s skin temperature beneath the vest. It can automatically regulate temperature by closed-loop control through processing skin temperature and  $T_{core}$  for safety and efficacy. The vest is novel as it is electrically powered, utilizing a lightweight transformer to thermoelectrically cool water (i.e.,

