The vest material is a lightweight, absorbent polymer that, if saturated with water, will use evaporation to provide additional heat loss over several hours (3-4 hrs). Most cooling vests are passive and use either conduction or evaporation to dissipate body heat. Our vest is designed to have the potential to selectively use either or both to restore some of the interrupted thermoregulatory function of conduction (vasodilation) and evaporation (sweating) in Veterans with Hi-SCI to optimize heat dissipation during ambient heat exposure. The inner lining of the vest is a thin, water-resistant material designed to minimize the user's clothing from getting wet. The large surface area of the cooling vest is designed to provide a sufficient interface for heat exchange to increase the rate of heat conduction from core to skin by lowering the expected skin temperature (~35°C) during heat challenge. Lowering skin temperature by 10-15°C serves to increase the temperature gradient between core and skin to increase the rate of heat dissipation from the body. The cool vest also functions as an insulator, preventing ambient heat from conducting heat into the user's torso.

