**Temperature Regulation with Feedback Control:** Suzurikawa et al. studied a “body heat removal system” utilizing thermo-electric cooling intended for persons with SCI and tested it in 5 AB participants. However, their device did not use closed-loop temperature control, only cooled the back, and they did not report further testing in persons with SCI. Power for our “smart” vest is modulated by a closed-loop feedback control loop to increase safety and efficacy. The microprocessor receives Tcore information from thermistor sensors taped to both axillae and skin temperature information from thermistor sensors taped to areas of the trunk with the greatest contact with the cool vest. Axillary measurements of Tcore are reliable and typically 1°C less than rectal measurement. Therefore, Tcore values of  $\geq 36.6^{\circ}\text{C}$  and  $\leq 35.4^{\circ}\text{C}$  will be used as thresholds to power on or off the vest, respectively. Threshold Tcore temperature values can also be manually entered, e.g.,  $\pm 0.5^{\circ}\text{C}$  from the user's measured baseline Tcore. Skin temperature values of  $>33^{\circ}\text{C}$  and  $<20^{\circ}\text{C}$  will be used to power on and power off the vest, respectively. Sensors monitoring circulating water temperature will also feed information to the microprocessor. All thermistors assess temperature every 5 seconds and information sent to the microprocessor is filtered to provide a moving average of the last ten measurements. The skin temperature threshold of  $<20^{\circ}\text{C}$  to power off the vest will override Tcore temperature to protect the skin from non-freezing cold injury, a safety feature designed to prevent non-freezing cold injury (skin temperatures  $< \sim 17^{\circ}\text{C}$  for prolonged periods) in persons with Hi-SCI who have insentient skin below their level of injury.

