overcome the time delay of temperature response. The control algorithm (implemented on a microprocessor with real-time control (A in Fig. 1) will have a three-layer neural network, including a hidden layer, thus combining the advantages of the standard proportional–integral–derivative (PID) control and a self-learning neural network. The input of the neural network includes reference temperature and body temperature sensor information. The three outputs of the hidden layer will be set as proportional P, integral I, and derivative units D, respectively. During system operation, the neural network is online-trained to automatically adjust the control parameters (P, I, D). The neural network will be able to learn the controller parameters (PID), resulting in more individualized thermal regulation for different users. [name] is experienced in human-in-the-loop control of human bio-systems, demonstrated by optimizing human performance with reinforcement learning-based optimal control algorithms. Picasso Intelligence will follow FDA guidelines for bench testing of medical devices to assess the performance of Prototype II. Key criteria include 1) accuracy of Tcore and skin temperature measurement (within 1°C), 2) responsiveness of closed-loop control (within 1°C), mass within 5 kg (target weight, 2.9 kg).

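### No stated control rule implements the promised 20°C vest floor, the 10–15°C design offset conflicts with it on its literal wording, and the skin cut-out equals the study's own failure and stop limit

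*Combined protocol and SAP*

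**What the plan says.** **The assurance (section 3c, Cooling Vest).** Feedback from multiple sensors is to "keep any material within its interior surface well above 17°C", the stated threshold for non-freezing cold injury on prolonged exposure. The paragraph then adds: "In an abundance of caution, the minimal vest temperature will be limited to" at least 20°C.

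**The design description (section 4, Preliminary Studies).** The vest offers a large contact area "with a material that is a good thermal conductor and will be maintained at a uniform temperature". The same sentence sets the offset at 10–15°C below the skin that the vest covers. It is meant to work "by lowering the expected skin temperature (~35°C) during heat challenge", and the text goes on to give the size of that fall: "Lowering skin temperature by 10-15°C serves to increase the temperature gradient between core and skin".

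**The control rules (section 4, Temperature Regulation with Feedback Control).**
- Axillary core temperature: on at 36.6°C or above, off at 35.4°C or below.
- Skin temperature: on above 33°C, off below 20°C. The skin threshold "to power off the vest will override Tcore temperature to protect the skin from non-freezing cold injury".
- Circulating water: sensed and sent to the microprocessor, with no threshold or action given.
- Filter: a reading every 5 seconds, averaged over the last ten.

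**The study limits (section 3).** Skin below 20°C under the vest fails the Phase 1 success criterion, defines vest failure in Sample Size and Statistical Approach, and ends a Phase 2 session. Section 3c uses the same value for removing the vest and terminating the protocol.

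**The bench criteria (end of section 4).** "Key criteria include 1) accuracy of Tcore and skin temperature measurement (within 1°C"), followed by closed-loop responsiveness within 1°C and a limit on mass.

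**The concern.** The risk section promises a limit on the temperature of the vest. The control section states limits on the temperature of the skin and the axilla. These are different quantities, and during active cooling the vest must be the colder of vest and skin. A reader of section 3c would believe that a vest floor is in force, yet section 4 does not show how it is enforced, and one of its design sentences points the other way.

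This matters most in Phase 2. Section 3c itself says that the cold-injury risk is greater in Hi-SCI because the skin is insentient, and the torso is monitored at 10 points there.

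The evaluation is affected too. Phase 1 counts participants with skin below 20°C, and Phase 2 stops a session at the same value. If the controller acts only at that value, vest failures and shortened sessions may reflect where the thresholds sit. The under-vest stop can shorten only the wet-vest condition, so it could also affect the comparison of the rise in core temperature between conditions.

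**Working it through.** **Inputs.** Vest floor 20°C and interior limit 17°C (section 3c). Vest 10–15°C cooler than the skin beneath it; uncooled skin about 35°C; intended fall in skin temperature 10–15°C; skin cut-out below 20°C; readings every 5 s averaged over ten; bench tolerance 1°C (all section 4).

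**1. Can the 20°C floor be reproduced?** The plan does not derive it. Its figures reach it only from uncooled skin: 35 − 15 = 20°C and 35 − 10 = 25°C, a vest at 20–25°C.

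**2. Literal reading of the offset.** Vest = skin − 15 to skin − 10.

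| Skin under vest (°C) | Implied vest (°C) |
|---|---|
| 35 (uncooled) | 20–25 |
| 33 (power-on threshold) | 18–23 |
| 32 | 17–22 |
| 30 | 15–20 |
| 27 | 12–17 |

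The vest equals 20°C at skin 20 + 15 = 35°C or 20 + 10 = 30°C. It equals 17°C at skin 17 + 15 = 32°C or 17 + 10 = 27°C. All four crossing points lie above the 20°C skin cut-out, so that cut-out would not have acted.

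**3. Single-drop reading.** If the 10–15°C is measured once, from skin at 35°C, the vest runs at 20–25°C and the floor is met. The intended skin range is also 35 − 15 to 35 − 10 = 20–25°C. Skin and vest could then differ by at most 25 − 20 = 5°C once skin reaches that range, which is not a material held 10–15°C cooler than the skin beneath it. The two sentences in section 4 therefore need reconciling with each other as well as with section 3c.

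**4. Can the skin cut-out enforce the vest floor?** A vest that is drawing heat from the skin is colder than the skin. When skin falls below 20°C under active cooling, the vest is already below 20°C. This holds whichever way the offset is read.

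**5. Margin to the study limit.** Cut-out minus failure/stop value = 20 − 20 = 0°C. The averaging window is 10 × 5 = 50 s. For a steady fall of r °C/min the mean lags by 4.5 × 5 = 22.5 s = 0.375 min, so true skin when the mean reaches 20°C is 20 − 0.375r. The plan gives no cooling rate. Assuming 0.2 to 2°C/min, the result is 19.925 to 19.25°C. The lower end of the intended skin range, 20°C, lies on the limit.

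**The case against.** The strongest reply is that silence is not contradiction. Section 3c states the vest floor and attributes it to several sensors, and water-temperature sensors that could carry such a limit are listed. No sentence claims that the skin rule delivers the vest floor. This stands to the extent that the floor may be intended and feasible; what is missing is a stated rule that implements it. It does not remove the conflict with the literal offset.

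Some stronger readings are tempting, and the documents do not support them:

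- **That the vest will run at 5–15°C.** This takes the intended skin of 20–25°C and subtracts 10–15°C a second time. The Prototype II description calls 10–15°C a range of temperature control, and the single-drop reading gives 20–25°C.
- **That the controller cannot act before cold injury.** The stated injury threshold is about 17°C for prolonged periods, 3°C below the cut-out. Taking off the full 1°C tolerance and the largest assumed lag leaves 20 − 1 − 0.75 = 18.25°C. The zero margin is to the study's precautionary limit.
- **That the vest floor is the only protection, or the skin rule the only power-off.** A T-shirt is worn under the vest, sentient AB participants test it first, and failure there sends it back to development. There is also an axillary power-off, although it bounds neither skin nor vest temperature.
- **That wet fabric keeps cooling the participant for hours after a stop.** The vest is removed when the limit is reached.
- **That no bench test of minimum temperature exists.** The list is introduced as what the key criteria include, so it is not exhaustive; FDA bench-testing guidance is cited, and validation of safety mechanisms is mentioned.

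One value for cut-out and study limit can also be defended as a conservative choice. But the controller's thermistors are separate from the study thermocouples, and a 1°C error can run either way, so the cut-out is still not set to act first.

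**Conclusion.** The point holds as a conflict between stated safety figures together with a missing control rule. Nothing in the control section enforces the vest floor of at least 20°C, and the stated skin cut-out cannot stand in for it while the vest is actively cooling. On the literal offset, the vest is below 20°C once skin is below 30–35°C and below 17°C once skin is below 27–32°C. On the single-drop reading it stays at 20–25°C, but the design sentence does not say that.

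Separately, the skin cut-out has 0°C of margin to the Phase 1 failure limit and the Phase 2 stop value, with a 1°C bench tolerance and a 50-second average.

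The offset result depends on which reading is meant. The lag figures depend on the assumed cooling rates. The zero margin depends on neither. The documents do not show that the floor is unachievable or that injury would follow. The point should be settled before anyone wears the vest, because the section 3c assurance is part of the safety case for participants with insentient skin.

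**What to change.** Before human testing, reconcile the Phase 1 procedure and the failure and stop definitions in section 3, the Cooling Vest paragraph of section 3c, and the design, control and bench paragraphs of section 4. The revised text should:

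- say which quantity the 20°C limit governs (skin, vest surface or circulating water), and from what the 10–15°C is measured;
- name the sensor and the control rule that enforce the vest floor in section 3c;
- say whether the closed-loop limits stay active when the vest runs at full power in Phase 1;
- reconcile the controller's skin cut-out with the failure and stop value in light of the stated sensor tolerance;
- list verification of the minimum interior-surface temperature among the bench criteria.

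The engineers and the study physician should choose all values; this point proposes none. The cost is protocol wording, possibly controller parameters, and one bench check. The possible downside is slightly less maximum cooling.
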